## SYNOPSIS

Title	Phase II Trial of Rucaparib in Patients with Metastatic and Non-Metastatic Hormone-Sensitive Prostate Cancer Harboring DNA Repair Gene Mutations (TRIUMPH)
Lead site	Johns Hopkins University
Sponsor	Clovis Oncology
IND holder	IND 137691(EXEMPT IND)
Investigational agent	Rucaparib 600mg by mouth twice daily, continuous dosing
Phase	2
Target population	

adult male > 18 years of age

Histologic or cytologic diagnosis of adenocarcinoma of the prostate.

Either (1) Metastatic disease as defined for one or more bone metastases confirmed by bone scintigraphy or radiographic soft tissue metastasis. Pelvic lymph nodes will be considered as metastatic disease if they measure <math>\geq 15</math> mm in short-axis diameter. Or (2) biochemically recurrence disease as defined by a PSA <math>>0.2</math> ng/ml post prostatectomy or a PSA rise of 2ng/ml or more from the nadir after radiation therapy.

Germline or somatic mutation in one or more homologous recombination DNA-repair genes (BRCA1, BRCA2, ATM, CHEK2, NBN, BRIP1, RAD50, RAD51C, RAD51D, PALB2, MRE11, FANCA, FANCB, FANCC, FANCD2, FANCE, FANCF, FANCG, FANCI, FANCL, FANCM) as documented by a clinical-grade, saliva, tissue, or blood based genetic test or molecular sequencing.

Patients must be informed about and must decline androgen deprivation therapy (ADT)-based systemic therapy

Serum PSA at screening <math>\geq 2.0</math> ng/mL

Serum testosterone level: <math>\geq 100</math> ng/dL at time of screening

patients with biochemical recurrence must have a PSADT <math>\leq 9</math> months, based upon <math>\geq 3</math> consecutive measurements collects in the past 12 months, at least 4 weeks apart, calculated using MSKCC calculator

life expectancy <math>>12</math> months

ECOG performance status <math>\leq 2</math>

Adequate bone marrow, renal and liver function (ANC <math>>1.5</math>K, Plt <math>>100</math>K, Hgb <math>>10</math> g/dL; Cr <math><1.5</math> mg/dL; AST/ALT <math>< 3</math>x ULN; Total Bilirubin <math><1.5</math>x ULN).

Study centers	Two sites in the United States
Start date/Duration	First patients are expected to be enrolled in March 2018. Accrual is estimated to last 2 years with up to 12 months of follow-up after the last patient has been entered.

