Expected enrollment	30 patients (Up to a max of 10 patients with non-BRCA1/BRCA2/ATM homologous recombination DNA-repair mutations allowed, ensuring at least 20 BRCA1/BRCA2/ATM-positive patients).
Rationale	
At the time of metastatic disease, continuous ADT (+/- docetaxel, +/- abiraterone) is commonly initiated for the treatment of prostate cancer. However, many men find it difficult to tolerate treatment-related toxicities, including sexual impotency, decreased libido, hot flashes, and weight gain. These symptoms can persist with the development of castration resistance. Treatment with non-AR targeted agents, such as PARPi, may avoid or delay the toxicities of hormonal therapy. Therefore, there is an unmet medical need to develop non-hormonal therapies for men with newly diagnosed metastatic prostate cancer who wish to avoid or defer the initiation of chronic ADT. There is also a similar need for those patients with biochemically recurrence prostate cancer at high risk of developing metastatic disease (i.e. PSADT <math>\leq</math> 9 months).
 
The clinical activity of PARPi in patients with homologous recombination DNA-repair mutations and metastatic prostate cancer has now been established. Focusing specifically on patients with an inactivating mutation in a pre-specified group of DNA-repair genes, we hypothesize that targeted therapy with PARPi should be sufficient to induce a clinical response irrespective of hormonal (castration-sensitive or castration-resistant) status. Our hypothesis is based largely on the data from Mateo et al (NEJM 2015) showing a clinical response rate to olaparib of 88% in a heavily pre-treated population of mCRPC patients with a DNA repair mutation, with the most pronounced responses being in men with germline inactivation.(1) For men with metastatic hormone sensitive prostate cancer (mHSPC) and high risk biochemically recurrent disease (BCR), this trial would also provide an alternative to ADT. However, given that primary ADT (in mHSPC and high risk BCR) is a standard first-line therapy, all patients on trial must be ineligible for or decline standard-of-care hormonal treatment. For patients with mHSPC who do not respond to PARPi, we have incorporated safety rules into the trial design to take patients off study at first signs of progression. Primary ADT (+/- docetaxel, +/- abiraterone) would still remain a treatment option upon progression.
 
The primary hypothesis of this study is that outcomes for patients with mHSPC and high risk BCR with an inactivating homologous repair mutation will be improved by this therapeutic agent (rucaparib)

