**Study design**

The study is an open-label single arm Phase II trial. Eligible patients are those with metastatic hormone-sensitive prostate cancer (mHSPC) or high-risk biochemically recurrent prostate cancer (BCR). All patients must have a documented germline or somatic mutation in a homologous recombination DNA-repair gene (BRCA1, BRCA2, ATM, CHEK2, NBN, BRIP1, RAD50, RAD51C, RAD51D, PALB2, MRE11, FANCA, FANCB, FANCC, FANCD2, FANCE, FANCF, FANCG, FANCI, FANCL, FANCM). Germline genetic testing and molecular sequencing as a screening for eligibility will not be offered. A mandatory tumor biopsy will be performed prior to the start of therapy in all patients with metastatic disease (if tumor material is not successfully obtained at the time of biopsy, then archival material will be sought). A second, OPTIONAL tumor biopsy will take place after three months of therapy.

After enrollment, patients will be treated with rucaparib at the established dose of **600mg by mouth twice daily**. Patients will be followed monthly with clinic visits, safety labs (including CBC w/diff, Comp), PSA, and toxicity assessments. Treatment [with a minimum drug exposure of 12 weeks] will be continued until PSA progression (PCGW3 criteria) or clinical/radiographic progression (whichever comes first), or until unmanageable toxicity requiring drug cessation. Patients who remain on treatment

for >12 months can begin to have their clinic visits, safety labs (including CBC w/diff, Comp), PSA, and toxicity assessments every 3 months.

A trial schema for study treatment appears below:

Criteria for evaluation

Primary Endpoint

- PSA50 response rate, defined as a decline in PSA to  $\geq 50\%$  of baseline level, confirmed with a second measurement at least 4 weeks later (PCWG3).

Secondary Endpoints

- Safety/Tolerability, defined as incidence of CTCAE v5.0 grade  $\geq 3$  toxicities experienced by patients on the trial.
- PSA progression-free survival, defined as a time from initiation on rucaparib therapy until PSA increase of 25%, confirmed with another measurement at least 4 weeks later (PCWG3).
- Radiographic progression-free survival (PCWG3): time to radiographic or clinical progression or death, whichever comes first. Based on RECIST version

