or death, and summarized using a Kaplan-Meier curve. Progression will be assigned to the earliest observed time. Patients whose disease has not progressed at follow-up will be censored at the date when the last tumor assessment determined a lack of progression. We will use the Kaplan-Meier method to estimate the median PFS.

*Objective response rate:*

The objective response rate is defined as the percentage of patients with measurable disease at baseline who achieve an objective response by RECIST1.1 criteria (i.e. Complete response or Partial Response) to rucaparib. We will estimate the objective response rate, along with the exact 95% confidence interval, for the population of patients.

Sample size/Power calculation:

The sample size is calculated to detect an improved PSA50 response rate from 50% to 75%. An optimal Simon two stage design is planned. A total of 12 patients will be entered in the first stage and the data analyzed for futility 12 weeks after the last patient begins rucaparib treatment. If 6 or fewer subjects have a PSA response, the study will be terminated and we will conclude the regimen is ineffective. If  $\geq 7$  subjects respond, then an additional 16 patients will be studied, for a total of 28 patients. If a total of 17 or fewer subjects respond in stage one and two combined, we consider this regimen ineffective. If a total of 18 or more respond, we conclude the regimen is promising and warrants further study. The maximum sample size will be increased to 30 patients to account for possible dropouts. The total number of patients allowed with a non-*BRCA1* or -*BRCA2* mutations will be capped at 10. This will ensure that at least 20 men will be enrolled with *BRCA1/BRCA2* mutations.

This design provides 90% power to detect an absolute 25% increase in PSA response rate with a one-sided type I error of 0.1. The probability of early stopping is 0.61 under the null hypothesis that the PSA response rate is 50%.

---

Safety analysis	Standard safety summaries will be provided for treatment exposure, patient disposition, adverse events leading to discontinuation, serious adverse events, and all events resulting in death, including those up to 30 days after treatment discontinuation. The incidence of adverse events will be tabulated and reviewed for potential significance and clinical importance.
-----------------	---

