### 3.2 Expected Enrollment

A total of 30 patients will be included in this study. Of these, we will include up to a maximum of 10 patients with non-*BRCA1* or -*BRCA2* mutations in this study. This will ensure a minimum of 20 men with *BRCA1/BRCA2* mutations. The first patients are expected to be enrolled in May 2018. Accrual is expected to be completed in 24 months once the protocol has been approved by the IRB at each participating institution.

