**10. STATISTICAL CONSIDERATIONS**

The primary endpoint will be the proportion of subjects who achieve a PSA response, defined as a 50% or greater decline in PSA from baseline, confirmed on a subsequent

measurement at least 3 weeks apart. The treatment regimen would be considered of insufficient activity for further study in this population if the PSA response rate is 50% or less. The sample size is calculated to detect an improved PSA response rate from 50% to 75%. An optimal Simon two stage design is planned. A total of 12 patients will be entered in the first stage with a planned analysis for futility performed 12 weeks after the last patient began rucaparib. The number of patients allowed with a non-BRCA1, -BRCA2, or -ATM mutation in stage 1 will be capped at 3. If 6 or fewer subjects have a PSA response, the study will be terminated and we will conclude the regimen is ineffective. If  $\geq 7$  subjects respond, then an additional 16 patients will be studied, for a total of 28 patients. If a total of 17 or fewer subjects respond in stage one and two combined, we consider this regimen ineffective. If a total of 18 or more respond, we conclude the regimen is promising and warrants further study. The maximum sample size will be increased to 30 patients to account for possible dropouts. The total number of patients (stage 1 and 2) allowed with a non-BRCA1/ -BRCA2 mutation will be capped at 10; this will ensure that at least 20 men will be enrolled with germline BRCA1/BRCA2 mutations.

This design provides 90% power to detect an absolute 25% increase in PSA response rate with a one-sided type I error of 0.1. The probability of early stopping is 0.61 under the null hypothesis that the PSA Response Rate is 50%.

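### Section 3.3 omits the synopsis PSA doubling-time limit for biochemical recurrence, the gene cap of 10 is stated in two incompatible ways, and a gene cap cannot deliver the germline floor in Section 10

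*Combined protocol and SAP*

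**What the plan says.** **PSADT.** The synopsis (Target population) makes a PSADT of 9 months or less mandatory for men with biochemical recurrence, and says how many PSA values are needed and which calculator to use. The synopsis Rationale defines high-risk recurrence by the same limit. The synopsis Study design and Section 2.1 both call the recurrent population high-risk. Section 3.3 defines recurrence only by PSA thresholds after surgery or radiation, and Section 3.1 says only that recurrent men are included. Section 4.1.1 has eligibility confirmed against Section 3, and Section 5.1 has it determined from the inclusion and exclusion lists.

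**Gene cap.** Four statements give a total cap of 10:
- Synopsis, Expected enrollment: "Up to a max of 10 patients with non-BRCA1/BRCA2/ATM homologous recombination DNA-repair mutations allowed, ensuring at least 20 BRCA1/BRCA2/ATM-positive patients".
- Synopsis, Sample size/Power calculation: "The total number of patients allowed with a non-*BRCA1* or -*BRCA2* mutations will be capped at 10", followed by "This will ensure that at least 20 men will be enrolled with *BRCA1/BRCA2* mutations".
- Section 3.2: "up to a maximum of 10 patients with non-*BRCA1* or -*BRCA2* mutations in this study", followed by "This will ensure a minimum of 20 men with *BRCA1/BRCA2* mutations".
- Section 10: a total cap of 10 on non-BRCA1/BRCA2 men, and "this will ensure that at least 20 men will be enrolled with germline BRCA1/BRCA2 mutations".

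Section 10 also has a separate stage 1 cap of 3, which groups ATM with BRCA1 and BRCA2.

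**Mutation origin.** The synopsis target population accepts "Germline or somatic mutation in one or more homologous recombination DNA-repair genes", and the study design says "All patients must have a documented germline or somatic mutation in a homologous recombination DNA-repair gene".

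**The concern.** These are rules on who may enter a trial of 30 men, and each should have one reading.

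The PSADT gap matters most. The section that sites are told to apply admits men whom the synopsis excludes. Slower recurrences could lengthen the median PSA progression-free survival, a descriptive single-arm estimate with no comparator to absorb the shift.

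The cap conflict can give opposite admission decisions for the same man. The primary result is one pooled PSA50 rate judged against fixed cut-offs (at least 7 of 12, then at least 18 of 28), so the gene mix matters if response differs by gene.

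The germline wording promises something that the rule beside it does not deliver.

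**Working it through.** **1. PSADT, text against text.** Take a man with recurrence after prostatectomy, PSA above the thresholds, and a PSADT longer than 9 months, who meets everything else.
- Synopsis, Target population: excluded.
- Section 3.3: every listed criterion is met, so included.
- Section 3.4: nothing excludes him.
- Sections 4.1.1 and 5.1: point to Section 3, so he is registered.

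The size of the effect cannot be computed. The documents give neither the share of men with biochemical recurrence nor the share of those with a PSADT above 9 months.

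**2. Cap arithmetic.** The plan's floor reproduces: 30 − 10 = 20. If enrolment stops at the design size it is 28 − 10 = 18. What the floor protects depends on the wording:
- Enrolment row of the synopsis: 20 BRCA1/BRCA2/ATM men. The cap alone guarantees no BRCA1/BRCA2 men, since all 20 could be ATM carriers.
- The other three statements: 20 BRCA1/BRCA2 men of any origin.
- Germline BRCA1/BRCA2 men: none guaranteed under either wording, because no rule limits somatic carriers.

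When the rules diverge: suppose 10 non-BRCA1/2 men are enrolled, say 6 with other genes and 4 ATM carriers. The enrolment row counts 6 toward the cap, so a further ATM carrier may enter. The other three count 10, so he may not. With fewer than 10 such men, neither total cap bars him.

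**3. Design check.** With X1 responders among the first 12 and X2 among the next 16:
- Early stopping at 50%: P(X1 ≤ 6) = 2510/4096 = 0.613 (plan: 0.61).
- Success: P(X1 ≥ 7 and X1 + X2 ≥ 18) = 0.081 at 50% (plan: limit 0.1) and 0.902 at 75% (plan: 90%).

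None of these involves the gene mix.

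**4. Gene mix, illustration only.** The same success probability was computed exactly, with X1 and X2 each a sum of independent binomials by gene group. Assumed PSA50 rates are 85% for BRCA1/2 and 50% for other genes; the documents give no such rates for this setting. Three men with other genes are in stage 1 (the stage 1 cap) and 7 in stage 2.
- No ATM carriers: 9 BRCA + 3 other, then 9 BRCA + 7 other. Success 0.886.
- Eight ATM carriers, 4 per stage: 5 BRCA + 4 ATM + 3 other, then 5 BRCA + 4 ATM + 7 other. Only the enrolment row allows this.

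| Assumed ATM rate | Success with 8 ATM carriers | Gap from 0.886 |
|---|---|---|
| 40% | 0.35 | 0.54 |
| 60% | 0.61 | 0.28 |
| 75% | 0.79 | 0.09 |
| 80% | 0.84 | 0.04 |
| 85% (same as BRCA) | 0.89 | 0 |

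The 80% row uses the only ATM figure in the documents: Section 1.3.1 reports a clinical response in 4 of 5 ATM carriers (4/5 = 80%). That was olaparib in castration-resistant disease, and the outcome was not PSA50, so it does not transfer directly. With 2, 4 or 6 ATM carriers at 80%, success is 0.875, 0.864 or 0.853.

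**The case against.** The intended population can be recovered. The synopsis says plainly that the PSADT limit is required, and the high-risk label recurs in Section 2.1. Registration is central (Section 4.1.2), supporting eligibility documents go to the lead site (Section 5.1), and an Eligibility Checklist form exists (Section 9.1.1). These lower the risk. They do not remove it, because the lead site's own instruction points to Section 3 and the checklist content is not shown.

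On the cap, three of four statements agree, including Sections 3.2 and 10; the outlier is one synopsis row. That is fair, but both versions stand in the same synopsis and no visible text says which governs.

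Four stronger readings are tempting, and the documents do not support them:
- *Sites could disagree about any ATM carrier.* The total caps conflict only after 10 non-BRCA1/2 men are enrolled.
- *The conflict costs the trial a fall in success probability from 0.89 to 0.61.* That needs an assumed ATM rate of 60% and 18 of 28 men without BRCA1/2 mutations. No gene mix in the documents makes this likely, and at 80% the gap is 0.04.
- *Section 10 contradicts itself because its stage 1 cap groups ATM differently.* The two caps can both be obeyed, and neither the stage 1 cap nor the floor of 20 is an error.
- *The germline wording damages an analysis.* No decision rule or planned analysis uses a germline count.

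**Conclusion.** All three inconsistencies stand in current text.

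- **PSADT, the main point.** Section 3.3 as written admits men whom the synopsis excludes. The possible consequence is a longer descriptive median PSA progression-free survival, of unknown size. A reader might infer a biased PSA50 decision, but nothing in the documents shows that.
- **Gene cap, second.** The two rules give opposite answers for an ATM carrier once 10 non-BRCA1/2 men are enrolled. The guaranteed BRCA1/BRCA2 floor at 30 men is 20 under three statements and zero under the cap in the fourth. The effect on the PSA50 decision is unknown, depends wholly on assumed rates, and vanishes if ATM and BRCA response are equal.
- **Germline, minor.** A one-word guarantee that a gene cap cannot give.

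The two-stage design is not in question: type I error 0.081, power 0.902 and early stopping 0.61 are unchanged. The first two items should be fixed. The case for that rests on the contradictory texts, not on the illustrative probabilities.

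**What to change.** 1. Reconcile Section 3.3 with the synopsis target population, so that the inclusion list sites use carries the PSADT criterion the synopsis already states. A matching line in Section 5.1 is optional.
2. Reconcile the synopsis enrolment row, the synopsis sample-size text, Section 3.2 and Section 10 to one grouping chosen by the sponsor, stating whether ATM carriers count toward the 10.
3. Reconcile the germline wording in Section 10 with the germline-or-somatic eligibility in the synopsis and with the floors in the synopsis sample-size text and Section 3.2.

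The cost is a short text amendment. Sample size, cut-offs and error rates stay as they are. Accrual may be somewhat slower once the PSADT limit is in the working list, and if ATM carriers are counted toward the 10. The documents give no figures to say by how much.

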## 10.1 Study Endpoints

### 10.1.1 Analysis of the primary endpoint

The primary endpoint of this study is PSA50 response, defined as a decrease in the PSA to 50% less than the baseline PSA upon enrollment in the trial. The decrease must be confirmed by a second measurement at least 4 weeks apart. For purposes of meeting the primary endpoint, patients will be considered to have done so if they have a PSA50 response only while on therapy with rucaparib. PSA values will be measured each cycle during the trial. All patients who are administered at least one dose of rucaparib will be considered evaluable for the primary endpoint. If patients do not have follow-up PSAs after initiation rucaparib therapy due to stopping therapy for toxicity or withdrawing consent, for example, then they will be replaced.

We will estimate the PSA50 response rate, along with the exact 95% confidence interval, for the population of patients.

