Subjects will have circulating tumor DNA (ctDNA) examined by FoundationACT testing before starting treatment and at clinical progression while on rucaparib. We will report the incidence and describe the observed reversion mutation, a known mechanism of resistance to PARP inhibition.

Statistical  
method

Primary Analysis

The primary endpoint of this study is PSA50 response, defined as a decrease in the PSA to  $\geq 50\%$  less than the baseline PSA upon enrollment in the trial. The decrease must be confirmed by a second measurement at least 4 weeks apart. For purposes of meeting the primary endpoint, patients will be considered to have done so if they have a PSA50 response only while on therapy with rucaparib. PSA values will be measured monthly during the trial. All patients who take at least one dose of rucaparib will be considered evaluable for the primary endpoint. If patients do not have follow-up PSAs after initiation rucaparib therapy due to stopping therapy for toxicity or withdrawing consent, then they will be replaced.

Secondary Analysis

*Safety:*

Patients will be assessed for toxicities at each clinical evaluation. Toxicities will be graded according to CTCAE v5.0 standardized grading scales. The incidence of grade 3-5 toxicities will be reported. Patients will be assessed for toxicity as long as they are taking rucaparib, and patients will continue to be followed if rucaparib is discontinued for toxicity until the toxicities improve to grade 1 or resolve. Toxicities will be reported as a tabulated table by type and grade.

*PSA progression-free survival (PSA-PFS):*

A standard definition of PSA progression per PCWG3 will be used. PSA-PFS will be defined as an increase in 25% over a nadir value, confirmed by a follow-up PSA at least 4 weeks later. If patients are removed from study prior to PSA progression, then they will be censored at that time. We will use the Kaplan-Meier method to estimate the median PSA-PFS.

*Radiographic progression-free survival (PFS):*

Progression-free survival will be measured from the time of first dose to objective clinical or radiographic tumor progression as defined by PCWG3 for progressive disease

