f C1D1 routine labs (CBC w/diff, Comprehensive Metabolic Panel, PSA, lipid panel) are only required if >7 days since screening labs.

g ctDNA will be collected once at before starting treatment and once at the time of progression.

- h In order to minimize the need for research-only in-person visits, telemedicine visits may be substituted for inperson clinical trial visits or portions of clinical trial visits where determined to be appropriate and where determined by the investigator not to increase the participants risks. Prior to initiating telemedicine for study visits the study team will explain to the participant, what a telemedicine visit entails and confirm that the study participant is in agreement and able to proceed with this method. Telemedicine acknowledgement will be obtained in accordance with the Guidance for Use of Telemedicine in Research. In the event telemedicine is not deemed feasible, the study visit will proceed as an in-person visit. Telemedicine visits will be conducted using HIPAA compliant method approved by the Health System and within licensing restrictions.
- I Patients who remain on treatment for >12 months can begin to have their clinic visits, safety labs (including CBC w/diff, Comp), PSA, and toxicity assessments every 3 months.

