## 5.2 Treatment/Intervention Period (Day 1 of each 28 day cycle +/- 3 days, ongoing)

Patients will be seen on D1 of each cycle of rucaparib (consisting of 28 days, +/- 3 days). The following assessments will be performed at each visit:

- conduct physical exam (including vital signs, weight)
- obtain any medical history changes from prior assessment
- assess performance status (ECOG). (Appendix A)
- review concurrent medications (see Appendix B for a listing of medications with the potential for drug interactions)
- Patients who remain on treatment for >12 months can begin to have their clinic visits, safety labs (including CBC w/diff, Comp), PSA, and toxicity assessments every 3 months.

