## 8.2 Therapeutic Response

Response and progression will be evaluated in this study using a combination of the international criteria proposed by the Response Evaluation Criteria in Solid Tumors (RECIST) Committee(17) and the guidelines for prostate cancer endpoints developed by the Prostate Cancer Clinical Trials Working Group (PCWG3).(18)

Patients will need to be reevaluated for response every cycle according to the guidelines below.

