#### 10.1.2.2. PSA progression-free survival (PFS)

A standard definition of PSA progression per PCWG3 will be used. PSA PFS will be defined as an increase in 25% over a nadir value, confirmed by a follow-up PSA at least 4 weeks apart. If patients are removed from study prior to PSA progression, then they will be censored at that time.

We will use the Kaplan-Meier method to estimate the median PSA PFS.

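### PSA is described as monthly throughout, yet may be 3-monthly after month 12: late PSA progressions are dated later, which can lengthen the median PSA-PFS if it lies near or beyond month 12

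*Combined protocol and SAP*

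**What the plan says.** Two parts of the combined protocol and SAP describe a constant PSA schedule:

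- Section 10.1.1: "PSA values will be measured each cycle during the trial".
- Synopsis, Primary Analysis: "PSA values will be measured monthly during the trial".

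Three parts allow a sparser schedule later:

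- Synopsis, Study design: patients remaining on treatment "for >12 months can begin to have their clinic visits, safety labs (including CBC w/diff, Comp), PSA, and toxicity assessments every 3 months".
- Table 1 (study calendar), last footnote: the same allowance, covering "safety labs (including CBC w/diff, Comp), PSA, and toxicity assessments every 3 months".
- Section 5.2: "Patients who remain on treatment for >12 months can begin to have their clinic visits", and the other listed assessments including PSA, at the 3-monthly interval.

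The allowance is permissive, and the documents do not say who decides.

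For PSA-PFS, Section 8.4.2 dates progression at the documented rise, with a confirming value 3 or more weeks later. Section 10.1.2.2 asks for confirmation at least 4 weeks apart, estimates the median by Kaplan-Meier, and adds: "If patients are removed from study prior to PSA progression, then they will be censored at that time". Section 5.5 schedules a PSA at the end-of-treatment visit, 28 days (plus or minus 3) after the last dose. No section says how PSA-PFS is dated or censored once visits are 3 months apart, or what happens to a qualifying rise with no confirming value.

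**The concern.** Median PSA-PFS is a secondary endpoint. A Kaplan-Meier analysis of visit-detected events treats the detection date as the event date. When the visit interval triples, detection comes later, and two men at month 15 may be on different schedules. The curve beyond month 12 then partly reflects the visit schedule.

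The censoring rule adds to this. A man with no recorded progression is credited with PSA-progression-free time up to removal, although nothing was measured after his last PSA, which may lie up to 3 months back. A man whose rise has been seen but not confirmed when he leaves is also censored at removal. Both tend to lengthen the estimate.

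**Working it through.** **Figures stated in the plan.** There is none for PSA-PFS. The only related figure is a median PFS of 9.8 months (Section 1.3.1), which concerns another drug (olaparib), castration-resistant disease and a different endpoint. The two-stage design for PSA50 does reproduce. At a 50% response rate, P(6 or fewer of 12) = 2510/4096 = 0.613 (stated 0.61). Type I error is 0.081 (limit 0.1) and power at 75% is 0.902 (stated 90%). The futility analysis takes place 12 weeks after the last stage 1 patient starts, so PSA after month 12 has almost no bearing on the primary endpoint.

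**Detection delay.** With visits a fixed interval apart, the mean delay is half the interval and the longest is the whole interval.

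| Schedule | Interval (months) | Mean delay | Longest delay |
|---|---|---|---|
| Every 28 days | 28/30.44 = 0.92 | 0.46 | 0.92 |
| Every 3 months | 3.0 | 1.5 | 3.0 |
| Difference | | 1.0 | 2.1 |

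**Who is exposed.** Under exponential times with median m, the share free of PSA progression at month 12 is 2^(-12/m): 0.43 at m = 9.8 (0.43 × 28, about 12 men) and 0.59 at m = 16. Treatment also ends for other reasons. With an assumed 2% per month of other removals, 0.43 falls to about 0.43 × 0.98^12 = 0.34.

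**Effect on the median: assumptions.** Visits every 28 days throughout were compared with 28-day visits to month 12 and 3-monthly visits after. Accrual was uniform over 24 months with 12 months of further follow-up (synopsis: 2 years, and up to 12 months). Not from the documents: true medians, Weibull shape 1.0 or 1.5, other removals 0 or 2% per month, every man taking the 3-monthly option, and no use of the end-of-treatment PSA for confirmation.

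*Large sample (N = 20,000), exponential, confirmation required, no other removals:*

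| True median | 28-day | 3-monthly after month 12 |
|---|---|---|
| 6 | 6.4 | 6.4 |
| 9.8 | 10.1 | 10.1 |
| 11 | 11.0 | 11.0 |
| 12 | 12.9 | 15.0 |
| 15 | 15.6 | 18.0 |
| 18 | 18.4 | 21.0 |

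Part of the jump from 12 months on arises because the estimate can only fall on a visit date. In the same setting the share of men with a counted event at a true median of 15 falls from 0.633 to 0.582.

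*Trial size (N = 28, 200 replicates per scenario), range over the scenarios:*

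| True median | Median unchanged | Mean shift (months) |
|---|---|---|
| 9.8 | 74 to 92% | 0.1 to 0.5 |
| 15 to 18 | 3 to 22% | 0.7 to 1.7 |

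At a true median of 6 the estimate did not move. With 28 men the estimated median can cross month 12 by chance, which is why there is some shift at 9.8.

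**Detection alone.** With 4,000 trials of 28 men, exponential times and no confirmation rule, the mean estimated median went from 10.54 to 10.86 (true 9.8), 13.80 to 14.58 (13) and 16.74 to 17.73 (16). The shifts are 0.3, 0.8 and 1.0 months. The standard deviation of the estimated median was 2.8 to 4.9 months.

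**Can the end-of-treatment PSA confirm?** It falls 25 to 31 days after the last dose. For a rise found on or before the last dosing day, that is at least 25 days later. This always meets 3 weeks (21 days) and misses 4 weeks (28 days) only if the rise was found in the last days of dosing and the visit is early.

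**The case against.** The strongest case against is that this is a wording mismatch with a small effect on a descriptive endpoint. Much of it stands.

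- A reader might infer that the 3-monthly schedule always pushes the median up. It does not. A median reached before about month 12 uses only data from the monthly period. In single trials the shift is not always upward either: at a true median of 16, one run of 2,000 trials gave an unchanged median in 20% and a lower one in about 11%, partly because the two visit grids do not nest.
- A reader might infer that the schedule itself forfeits confirmation. It does not. Sections 8.4.2 and 10.1.2.2 set a minimum gap and no maximum, so a value 3 months later confirms, and Section 8.4.2 keeps the date at the first rise. Confirmation is at risk only if the man leaves or reaches the data cut-off first, and the end-of-treatment PSA can often supply it. Section 8.2.1 does not bar an earlier repeat, and for men with no decline Sections 8.1.2.2 and 8.4.2 state no confirmation requirement.
- Because the monthly statement sits in the primary-endpoint section, a reader might infer that PSA50 is compromised. It is not.
- PSA-PFS has no comparator, threshold or test, and the shift is small beside the sampling variation of the estimate.

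What the objection does not remove: the texts conflict, progressions after month 12 are dated later wherever the median lies, Section 10.1.2.2 does not say whether the end-of-treatment PSA counts, and censoring at removal credits time without PSA data.

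**Conclusion.** The concern holds as a minor point about a secondary endpoint. The schedules contradict each other, and the PSA-PFS rules do not allow for the sparser one. After month 12, progressions are dated about 1 month later on average. The Kaplan-Meier median can rise by about 0.7 to 1.7 months with 28 men if the true median is 15 to 18 months, and by little or nothing if it is below about 11. These sizes depend on the assumed time distributions and on every man taking the 3-monthly option; with partial uptake they would be smaller. Since the documents give no expected PSA-PFS, neither a median beyond month 12 nor one before it can be presumed.

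**What to change.** 1. Reconcile the synopsis Primary Analysis text and Section 10.1.1 with the synopsis study design, the Table 1 footnote and Section 5.2, so that the analysis text describes the schedule actually allowed. Which schedule to keep is for the sponsor.
2. In Section 10.1.2.2, censor men without PSA progression at their last PSA rather than at removal, and state that the end-of-treatment PSA may confirm an earlier rise.
3. Add a sensitivity analysis that treats PSA progression as interval-censored between the last PSA without progression and the first qualifying PSA, and that counts a qualifying but unconfirmed rise as an event. Report it beside the Kaplan-Meier median, at least if that median is near or beyond 12 months.

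In a simulation with 28 men, censoring at the last PSA together with counting unconfirmed rises as events removed up to about 0.5 month of upward bias. The cost is some wording and one extra analysis of data already collected, and the stated median may become slightly shorter.
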